2. STUDY DESIGN

Figure 1 Study design

D: Day; **FU:** follow-up; **IDMC:** Independent Data Monitoring Committee; **iSRC:** internal Safety Review Committee; **RSV:** respiratory syncytial virus; **RTI:** respiratory tract infection; **SE:** solicited events; **V:** Visit **1D:** 1 Dose (1.5×10^{10} vp/dose); **2D:** 2 Dose (5×10^{10} vp/dose); **FB:** Formulation buffer S9b.

* Vaccine Dose 1 at Day 1 will be administered before the first RSV season (refer to Section 5.1 of the protocol for definition of RSV season).

† Visit 2 (Day 8), Visit 4 (Day 38), and Visit 8 (no blood sampling for immune response and no vaccine administration) may take place in the subject's home or at the investigators clinical facility as appropriate to the circumstances in the judgment of the investigator. For authorized sites only, Visit 5 (Day 61) and Visit 7 (both with blood sampling) may also take place in the subject's home or at the investigators clinical facility as appropriate to the circumstances in the judgment of the investigator.

‡ In countries where Mencevo or Placebo is used as a comparator, no administration will be performed at Day 121 and therefore in those countries there will be no Visit 6 and it will be administered at the end of the first RSV season at Visit 7 (refer to Table 2 and Table 7 of the protocol).

a Surveillance for RSV-RTI comprises monthly nasal swab collected to detect asymptomatic RSV infections during RSV season and active and passive surveillance contacts for RSV symptomatic RTI. Of note the swab may be omitted if a nasal swab has been taken at a symptomatic visit in the same month (see Section 9.2 of the protocol). Data about RSV-RTI incidence will be reviewed monthly by an IDMC.

b An iSRC will review all accumulating safety data monthly until the IDMC reviews has reviewed all safety data up to 30 days after administration of Dose 2 (i.e., Day 61). The IDMC will review all accumulating safety data monthly throughout the period of vaccination and accumulating SAEs until the end of the second RSV transmission season.

Refer to Sections 9.10.2 and 9.10.3 of the protocol.

c Refer to Section 6.6.12.3 of the protocol

Table 1 Vaccines administered and vaccination schedules

Groups	Age* (Months) / (Visit, Day)				
	6-7 / (V1, D1)	7-8 / (V3, D31)	8-9 / (V5, D61)	10-11 / (V6, D121)**	14-18 / (V7)
1D RSV + Bexsero	1D RSV ChAd	FB	Bexsero	Bexsero	Bexsero
2D RSV + Bexsero	2D RSV ChAd	2D RSV ChAd	Bexsero	Bexsero	Bexsero

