- Study visits: Other than the screening visit and assessment visits for active/passive surveillance, there will be 8 study visits except in countries where *Menveo* or Placebo is used as a control where there will be 7 study visits.
 - In countries where *Menveo* is used as a comparator, no administration will be performed at Day 121 and therefore in those countries there will be no Visit 6 and it will be administered at the end of the first RSV season at Visit 7 (refer to Table 2 and 7 of the protocol).
 - In countries where Placebo is used as a control, no vaccine administration will be performed after Visit 3 and therefore in those countries there will be no Visit 6. There will be a Visit 5 and Visit 7 for countries using Placebo and all other study procedures will occur at these visits except vaccination.
 - Visit 2 (Day 8), Visit 4 (Day 38), and Visit 8 (no blood sampling for immune response and no vaccine administration) may take place in the subject's home or at the investigators clinical facility as appropriate to the circumstances in the judgment of the investigator.

- For authorized sites only, Visit 5 (Day 61) and Visit 7 (both with blood sampling) may also take place in the subject's home or at the investigators clinical facility as appropriate to the circumstances in the judgment of the investigator.
- Data collection: electronic Case Report Form (eCRF).
- Safety monitoring: internal safety review committee (iSRC) and IDMC (refer to Section 9.10 of the protocol).
- **Surveillance for RSV-RTI, difficulty in breathing, and wheezing episodes**
Surveillance period will be carried out from Visit 1 (after Dose 1) until the last study visit (end of the second RSV transmission season). In order to detect asymptomatic RSV-RTI, monthly nasal swabs for analysis at sponsor laboratory will be performed for all subjects during the RSV season. In order to timely detect RSV-RTI and to ensure cases are timely captured by the study sites, both active and passive surveillance will be conducted:
 - **Passive surveillance:** parent(s)/LAR(s) are instructed to contact the investigator/study staff as soon as the subject experiences new RTI symptoms (cough, runny nose or blocked nose) or worsening of RTI symptoms, or in case of difficulty in breathing or wheezing.

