The incidence rate of asymptomatic RSV infections (with 95% CI) detected by the quantitative PCR (RSV-A/B), will be tabulated by the three pooled groups. Descriptive analyses (mean, median, min, max) of viral load assessed by the quantitative RT-PCR (RSV-A/B) of those asymptomatic RSV infections will also be done on the three pooled groups.

The RVP (Multiplex PCR) on specimens from all RSV-A/B positive and confirmed LRTI cases, according to case definition presented in Table 6 (Figure 3 of the protocol for the decision tree), will be tabulated as a qualitative assessment profiling the potential co-infections occurring in these subjects.

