9.2. RTI and LRTI

During the analysis of the study, all cases identified during the surveillance of RSV-RTI will be definitively classified as either RTI, LRTI, severe LRTI or very severe LRTI according to the standardized case definitions (Table 6 in the SAP) based on the available World Health Organization (WHO) case definitions (Table 6 in the protocol)

Table 6 Case definitions for data analysis

Case	At sea level up to 2500 meters elevation	Above 2500 meters elevation
RSV-RTI	Runny nose OR blocked nose OR cough AND Confirmed RSV infection ⁴	Same
RSV-LRTI	History of cough OR difficulty breathing ¹ AND SpO ₂ < 95% ² , OR RR increase ³ AND Confirmed RSV infection ⁴	Same but with SpO₂ < 92%
severe RSV-LRTI	Meeting the case definition of RSV-LRTI AND SpO ₂ < 93% ² , OR lower chest wall in-drawing	Same but with SpO₂ < 90%
very severe RSV-LRTI	Meeting the case definition of RSV-LRTI AND SpO ₂ < 90% ² , OR inability to feed, OR failure to respond / unconscious	Same but with SpO₂ < 88%

Case	At sea level up to 2500 meters elevation	Above 2500 meters elevation
RSV hospitalization	Confirmed RSV infection ⁵ AND Hospitalized for acute medical condition ⁶	Same
All-cause LRTI	History of cough OR difficulty breathing ¹ AND SpO ₂ < 95% ² , OR RR increase ³	Same but with SpO₂ <92%

LRTI = lower respiratory tract infections; RR = respiratory rate; RTI = respiratory tract infections; SpO₂ = blood oxygen saturation.

¹ Based on history reported by parents.

² The lowest value during the course of illness will be used.

³ RR increase defined as:≥ 50/minute (2 to 11 months of age) ; ≥ 40/minute (12 months of age or above) ;
The highest value during the course of the illness will be used.

⁴ RSV infection confirmed on nasal swab positive for RSV A or B by quantitative Reverse Transcription Polymerase Chain Reaction (qRT-PCR).

⁵ RSV sampling and testing is based on medical judgment of medical practitioner or driven by algorithm.

⁶ Hospitalization is defined as a medical decision that the infant requires admission for observation or treatment.

- For the analysis of RTI episode, a new RTI episode will be defined as any occurrence of cough, runny nose, blocked nose, wheezing or difficulty breathing with an interval of at least 7 symptom free days since the last episode of RTI that was diagnosed.
- For molecular biology (qRT-PCR test), the following cut-off will be applied: -

System	Component	Method	Unit	Cut-off

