N= number of subjects with at least one RSV infection (symptomatic or asymptomatic)

n/% = number/percentage of subjects reporting at least one RSV hospitalization

95%CI= Exact 95% confidence interval; LL = lower limit, UL = upper limit

Template 41 Number and percentage of subjects reporting the RSV infection of different severity (based on WHO case definition) by number of events experienced between vaccination dose 1 up to end of <first, second> RSV season for pooled RSV 1D, RSV 2D and Comparator/Placebo group <Exposed Set, Exposed Set with negative RSV baseline status>

Characteristics	Categories	<Each group> N=xx				
		n	%	95% CI	LL	UL
RSV infection-symptomatic or asymptomatic*	0					
	1					
	2					
RSV-RTI	0					
	1					
RSV-LRTI	0					
	1					
	2					
RSV-Severe LRTI	0					
	1					
RSV-very severe LRTI	0					
	1					
All cause LRTI	0					
	1					
	2					
	3					
RSV hospitalization\$	0					
	1					
	2					
	3					

Short group label = long group label

N = number of subjects in each group

n = number of subjects in a given category

% = $100 * n / N$

LL, UL for percentage = Exact 95% Lower and Upper confidence limits

Please note – Single episode can be considered in multiple category depending on the symptom experienced

* Association to RSV based on central testing only for asymptomatic visit (no local test available)

\$Confirmed RSV infection and hospitalized for acute medical condition

Template 42 Number and percentage of RSV infections and associated disease severity (based on WHO case definition) and relative risk from vaccination dose 1 up to end of <first, second> RSV season for pooled RSV 1D, RSV 2D and Comparator/Placebo group <Exposed Set, Exposed Set with negative RSV baseline status>

Categories	<Each Group> N =		Relative risk (RSV1D vs Comparator/Placebo)				Relative risk (RSV2D vs Comparator/Placebo)			
			95% CI		95% CI				95% CI	
	n	%	LL	UL	Values	LL	UL	Values	LL	UL
RSV asymptomatic (Excluding RSV-RTI, LRTI, RSV-severe LRTI or RSV-very severe LRTI)										
RSV RTI (Excluding LRTI, RSV-severe or very severe LRTI)										
RSV LRTI (Excluding RSV-severe or very severe LRTI)										
RSV-severe LRTI (Excluding RSV-very severe LRTI)										
RSV-very severe LRTI										

Short group label = long group label

* Association to RSV based on central testing only for asymptomatic visit (no local test available)

N = number of RSV positive samples in each group

n** = number of cases in each category

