Please note: each episode for a subject is considered to be independent. We may have multiple swab for one episode.

We have considered the swab with maximum viral load from one episode for the table

Please note – Except for RSV hospitalization, single episode is considered in single category of highest severity based on the symptom experienced

Please check:- To check for cases where asymptomatic swab has been taken but the subject hasve symptoms of RTI or LRTI. In this case, asymptomatic is also considered as RSV RTI/LRTI and maximum viral load of all the episode should be considered.

Template 45 Descriptive statistics of maximum viral load per subjects based on qRT-PCR confirmed episode with varying disease severity (based on WHO case definition) from vaccination dose 1 up to end of <first, second> RSV season for pooled RSV 1D, RSV 2D and Comparator/Placebo group <Exposed Set, Exposed Set with negative RSV baseline status>

Symptoms	Parameters	Each Group N=		
		95% CI		
RSV asymptomatic* (Excluding RSV-RTI, RSV-LRTI, RSV-severe LRTI or RSV-very severe LRTI)	n			
	GM			
	95% CI			
	SD			
	Q1			
	Median			
	Q3			
RSV RTI (Excluding RSV-LRTI, RSV-severe or RSV-very severe LRTI)	Min/Max			
	...			
RSV LRTI (Excluding RSV-severe or RSV-very severe LRTI)	...			
RSV-severe LRTI (Excluding RSV-very severe LRTI)	...			
RSV-very severe LRTI	...			
RSV hospitalization\$...			

Short group label = long group label

N = number of RSV positive subjects in each group

n= Number of subjects in each category

SD=Standard Deviation

Q1 and Q3 = 1st and 3rd quantiles

Min/Max = Minimum/Maximum

GM = Geometric mean

LL, UL for GM = Exact 95% Lower and Upper confidence limits

Total RSV viral load computed as RSV A Viral load + RSV B Viral load

Please note: Except of RSV hospitalization, the subject has been considered only once in one of the category based on the maximum severity of event experienced

* Association to RSV based on central testing only for asymptomatic visit (no local test available)

\$Confirmed RSV infection and hospitalized for acute medical condition

Template 46 Frequency of multiple respiratory pathogen for qRT-PCR confirmed RSV-RTI episodes from vaccination dose 1 up to end of <first, second> RSV season for pooled RSV 1D, RSV 2D and Comparator/Placebo groups <Exposed Set, Exposed Set with negative RSV baseline status>

Categories	Group N =				Total N =			
			95% CI				95% CI	
	n	%	LL	UL	n	%	LL	UL
Influenza Virus A/California/7/2009(H1N1)								

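### An RSV infection that stays PCR-positive after symptoms end can be counted more than once in the event-level tables

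*SAP*

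**What the plan says.** Three parts of the SAP together determine what is counted as an RSV infection.

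- **Separation of episodes (Section 9.2).** A new RTI episode is any recurrence of the listed respiratory symptoms "with an interval of at least 7 symptom free days since the last episode of RTI that was diagnosed". The rule rests on symptoms alone.
- **Confirmation (Section 9.2, Table 6, footnote 4).** "RSV infection confirmed on nasal swab positive for RSV A or B by quantitative Reverse Transcription Polymerase Chain Reaction (qRT-PCR". No interval, intervening negative swab or change of subtype is required.
- **Sampling (Section 2).** Besides swabs at symptomatic visits, "monthly nasal swabs for analysis at sponsor laboratory will be performed for all subjects during the RSV season". Footnote a to Figure 1 adds that "the swab may be omitted if a nasal swab has been taken at a symptomatic visit in the same month".

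On outputs, Section 5.4.1 tabulates the number of RSV infections per group and states: "The incidence rate of asymptomatic RSV infections (with 95% CI) detected by the quantitative PCR (RSV-A/B), will be tabulated by the three pooled groups". In the mock tables, the notes to Template 44 say that "each episode for a subject is considered to be independent", that one episode may have several swabs, and that the swab with the highest viral load represents the episode. They also fold a routine swab into the RTI or LRTI when the child has symptoms at the time. Template 42, which shows severity percentages and relative risks by arm, has the footnote "N = number of RSV positive samples in each group", while another of its notes places each episode in one severity category.

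**The concern.** The symptom rule cannot separate or join asymptomatic positives, and it ignores whether the virus is the same one. Two routes to repeat counting are open:

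1. An infant has an RSV-RTI, recovers, and is still PCR-positive at a later monthly swab. That swab can enter as an asymptomatic infection.
2. An infant is well for seven days and then catches another cold while RSV is still detectable. That can enter as a second RSV-RTI.

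The SAP expects repeats: Template 41 has a row for two RSV infections and Template 51 a row for two asymptomatic infections. It does not say when a second positive is a second infection. At stake are the count of infections per arm and the share of infections that are severe, in a trial that follows infants for enhanced disease. Two programmers following this text could produce different tables.

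**Working it through.** **No figure to reproduce.** The SAP states no shedding time, expected number of infections or repeat share. What follows checks the text, then illustrates on assumed values.

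**Which outputs are exposed**

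| Output | Unit | Exposed? |
|---|---|---|
| Number of RSV infections (5.4.1) | event | yes |
| Asymptomatic incidence (5.4.1) | not stated | yes, if counted per event |
| Template 42 | N = positive samples, rows = episodes | yes, most directly |
| Template 44 | episode | yes |
| Template 46 | RSV-RTI episode | yes, by route 2 |
| Template 50, n** | case | yes |
| Templates 41 and 51 | infants by number of events | repeat-event rows |
| Template 43 | N = RSV infections, no asymptomatic row | to the extent that N includes repeat positives |
| Templates 39, 40, 45, 57 | infant | no |
| Relative risks for at least one event (5.4.1) | infant | no |
| Very severe RSV-LRTI rate (5.4.1, Section 6) | infected infant | no |

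**Route 1: a positive monthly swab after recovery.** Assumptions: swabs every 30 days at a random phase, symptoms for S = 7 days from the start of shedding, shedding for D = 14 or 21 days, so 7 or 14 days of positivity after symptoms end.

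- No same-month swab omitted: probability = (D − S)/30, that is 7/30 = 0.23 and 14/30 = 0.47.
- Same-month swab always omitted (simulation, symptomatic swab on day 3): 0.06 and 0.17.

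For 20 symptomatic infections:

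| Positivity after symptoms | Omission | Extra infections | LRTI share if 6 of 20 are LRTI |
|---|---|---|---|
| 7 days | always | 20 × 0.06 ≈ 1 | 6/21 = 29% |
| 14 days | always | 20 × 0.17 ≈ 3 | 6/23 = 26% |
| 7 days | never | 20 × 0.23 ≈ 5 | 6/25 = 24% |
| 14 days | never | 20 × 0.47 ≈ 9 | 6/29 = 21% |

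The undiluted share is 6/20 = 30%.

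**Route 2: a new cold while still positive.** With an assumed 0.5 new RTIs per month, probability = 1 − exp(−0.5 × (D − S − 7)/30). For S = 7 this is 0 at D = 14 and 1 − exp(−0.5 × 7/30) = 0.11 at D = 21, about 0 to 2 per 20 infections. These are not included in the 1 to 9 above.

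**Purely asymptomatic infection.** Two positive monthly swabs need more than 30 days of detectable shedding. The probability is (D − 30)/30 for D between 30 and 60: 0 at 30 days, 0.33 at 40 and 0.50 at 45.

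**Template 42 denominator.** With 20 infections of which 2 are very severe, the share is 2/20 = 10.0%. With 2, 5 or 10 repeat positive samples in N it becomes 2/22 = 9.1%, 2/25 = 8.0% or 2/30 = 6.7%.

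**Between arms.** If repeats add a fraction a in vaccinees and b in controls, a true event ratio of 1 appears as (1 + a)/(1 + b). Equal fractions (0.3 and 0.3) give 1.00; 0.1 and 0.3 give 1.1/1.3 = 0.85; 0.3 and 0.1 give 1.3/1.1 = 1.18.

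**The case against.** The strongest reply is that the plan already has safeguards and that the important results do not depend on event counts.

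- **Safeguards.** Template 44 merges swabs taken during symptoms and keeps one swab per episode. A reader might infer that every positive monthly swab becomes its own infection; these notes show that it does not. But they do not reach a positive swab taken after recovery, and the merging note is still worded as a point to check.
- **Omission of the monthly swab.** This cuts the size considerably, as the table shows. It is optional and limited to the same month, so it does not close the gap.
- **PCR cut-offs.** Section 9.2 sets 1.12 × 10³ copies/ml for RSV-A and 1.47 × 10³ for RSV-B. These may drop low residual RNA and shorten the window. They do not link positives above the cut-off.
- **Season.** Monthly swabs run only in the RSV season, defined as the period with 70% of cases in previous years. Infections outside it can escape route 1, so the estimates apply to in-season infections.
- **Main readouts.** The criterion in Section 6 and the relative risks for at least one event count each infant once, and Section 6 calls comparative analyses exploratory. This stands in full and limits the point to event-level outputs.
- **Left to the protocol.** Section 5 of the SAP assigns study-specific derivation rules to Section 9, so an infection definition belongs there.

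**Conclusion.** The point holds for event-level results. As written, the rules allow one RSV infection to be counted more than once, and Template 42 mixes samples with episodes. On the assumed 7 to 14 days of positivity after symptoms end, 20 symptomatic infections gain about 1 to 9 spurious ones and a 30% LRTI share falls to between about 29% and 21%. The range reflects both shedding time and how often same-month swabs are skipped; neither is given in the SAP.

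A reader might infer two stronger conclusions, which the documents do not support. The first is that infections will be double counted as a matter of course: this depends on shedding time, and can be said only as a possibility. The second is that the arm with more illness has its severity share diluted, so that enhanced disease is hidden. Proportional repeats dilute both arms equally. A difference arises only if repeat shares differ by arm, and it can go either way, so no direction of bias can be claimed.

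This should be settled before the event-level tables are produced. It does not touch the per-infant safety conclusion.

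**What to change.** In Section 9.2, define an RSV infection virologically, for positives from symptomatic and asymptomatic visits alike:

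- A positive swab belongs to the previous infection if it is the same subtype (A or B), no RSV-negative swab lies between the two, and the gap since the last positive is within a prespecified window. Otherwise it starts a new infection.
- The window must exceed one monthly swab interval, for example 45 days. A 30-day cut-off could still split two consecutive monthly positives. Add a sensitivity analysis on the window.
- The linked infection keeps its highest severity and highest viral load. It is asymptomatic only if no RTI symptoms are recorded in it.
- Change the Template 42 denominator from positive samples to linked infections. Apply the rule to Templates 41, 42, 43, 44, 46, 50 (n**) and 51 and to asymptomatic incidence.

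The cost is one derivation rule using swab dates and RSV-A/B results that are already collected, plus footnote changes. The downside is that a rare true reinfection with the same subtype inside the window would be merged; the sensitivity analysis shows how much that matters.

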9.3. Hematology and Biochemistry parameters

The grading of the hematology and biochemistry lab result will be done as per the toxicity grading scales provided in the Table 7 below (Table 28 of the protocol).

Table 7 Toxicity grading scales for hematology and biochemistry parameters applicable for this study

Component	Grade 1	Grade 2	Grade 3	Grade 4
Hemoglobin (g/dL)	9.0 to < 10.5	8.0 to < 9.0	7.0 to < 8.0	< 7.0
Leukocytes (cell/mm ³)	2500 to < 3500	1500 to < 2500	1000 to < 1500	< 1000
Absolute neutrophil count (cell/mm ³)	1000 to < 1300	750 to < 1000	500 to < 750	< 500
Absolute lymphocyte count (cell/mm ³)	600 to < 650	500 to < 600	350 to < 500	< 350
Platelets (cell/mm ³)	75000 to < 150000	50000 to < 75000	25000 to < 50000	< 25000
Alanine Aminotransferase (increase by factor)	1.1 to < 2.0 xULN	2.0 to < 3.0 xULN	3.00 to ≤ 8.0 xULN	> 8.0 xULN
Aspartate Aminotransferase (increase by factor)	1.1 to < 2.0 xULN	2.0 to < 3.0 xULN	3.00 to ≤ 8.0 xULN	> 8.0 xULN
Creatinine (mg/dL)	0.6 to < 0.9	0.9 to < 1.2	1.2 to ≤ 1.5	> 1.5

ULN: upper limit of normal.

9.4. Coding for the AE of specific interest

Any of the below listed preferred term reported as an Expedited Adverse Event must be immediately escalated to the CRDL or Central Safety Physician to assess or confirm the need for an urgent IDMC review.

The list of preferred terms and associated PT codes is given below:

HAEMATOMA

Preferred term	PT code
abdominal wall haematoma	10067383
administration site haematoma	10075100
adrenal haematoma	10059194
aortic intramural haematoma	10067975
application site haematoma	10068317
arterial intramural haematoma	10074971
auricular haematoma	10003797
basal ganglia haematoma	10077031
brain stem haematoma	10073230
breast haematoma	10064753
broad ligament haematoma	10006375
bursal haematoma	10077818
catheter site haematoma	10055662
cephalhaematoma	10008014
cerebellar haematoma	10061038
cerebral haematoma	10053942
cervix haematoma uterine	10050020
chest wall haematoma	10076597
colonic haematoma	10009996
deep dissecting haematoma	10074718
extradural haematoma	10015769
eyelid haematoma	10064976
haematoma	10018852
haematoma evacuation	10060733
haematoma infection	10051564
hepatic haematoma	10019676
incision site haematoma	10059241
infusion site haematoma	10065463
injection site haematoma	10022066
instillation site haematoma	10073609
intestinal haematoma	10069829
intra-abdominal haematoma	10056457
intracerebral haematoma evacuation	10062025

Preferred term	PT code
intracranial haematoma	10059491
intraocular haematoma	10071934
laryngeal haematoma	10070885
lip haematoma	10066304
mediastinal haematoma	10049941
medical device site haematoma	10075577
mesenteric haematoma	10071557
nasal septum haematoma	10075027
oesophageal intramural haematoma	10077486
oral mucosa haematoma	10074779
ovarian haematoma	10033263
paranasal sinus haematoma	10069702
pelvic haematoma	10054974
penile haematoma	10070656
perineal haematoma	10034520
periorbital haematoma	10034544
periosteal haematoma	10077341
perirenal haematoma	10049450
peritoneal haematoma	10058095
pharyngeal haematoma	10068121
post procedural haematoma	10063188
pulmonary haematoma	10054991
renal haematoma	10038459
retroperitoneal haematoma	10058360
scrotal haematoma	10039749
spinal cord haematoma	10076051
spinal epidural haematoma	10050162
spinal subdural haematoma	10050164
splenic haematoma	10041646
spontaneous haematoma	10065304
subarachnoid haematoma	10076701
subcutaneous haematoma	10042345
subdural haematoma	10042361
subgaleal haematoma	10069510
subretinal haematoma	10071935
tongue haematoma	10043959
uterine haematoma	10063875
vaccination site haematoma	10069472
vaginal haematoma	10046909
vitreous haematoma	10071936
vulval haematoma	10047756

HAEMORRHAGE

Preferred term	PT code
abdominal wall haemorrhage	10067788
acute haemorrhagic conjunctivitis	10067817
administration site haemorrhage	10075101
adrenal haemorrhage	10001361
anal haemorrhage	10049555
anastomotic haemorrhage	10056346
angina bullosa haemorrhagica	10064223
application site haemorrhage	10072694
arterial haemorrhage	10060964
basal ganglia haemorrhage	10067057
bone marrow haemorrhage	10073581
brain stem haemorrhage	10006145
brain stem microhaemorrhage	10071205
breast haemorrhage	10006254
bronchial haemorrhage	10065739
catheter site haemorrhage	10051099
central nervous system haemorrhage	10072043
cerebellar haemorrhage	10008030
cerebellar microhaemorrhage	10071206
cerebral haemorrhage	10008111
cerebral microhaemorrhage	10067277
cervix haemorrhage uterine	10050022
ciliary body haemorrhage	10057417
conjunctival haemorrhage	10010719
diverticulitis intestinal haemorrhagic	10013541
diverticulum intestinal haemorrhagic	10013560
duodenitis haemorrhagic	10013865
ear haemorrhage	10014009
encephalitis haemorrhagic	10014589
gastric haemorrhage	10017788
gastroduodenal haemorrhage	10053768
gastrointestinal haemorrhage	10017955
genital haemorrhage	10061178
haemarthrosis	10018829
haematemesis	10018830
haematochezia	10018836
haematotympanum	10063013
Haematuria	10018867
haemorrhage	10055798
haemorrhage coronary artery	10055803

Preferred term	PT code
haemorrhage intracranial	10018985
haemorrhage subcutaneous	10018999
haemorrhage subepidermal	10019001
haemorrhage urinary tract	10055847
haemorrhagic anaemia	10052293
haemorrhagic diathesis	10062713
haemorrhagic disorder	10019009
haemorrhagic infarction	10019013
haemorrhagic ovarian cyst	10060781
haemorrhagic pneumonia	10077933
haemorrhagic thyroid cyst	10072256
haemorrhagic urticaria	10059499
injection site haemorrhage	10022067
internal haemorrhage	10075192
intestinal haemorrhage	10059175
intra-abdominal haemorrhage	10061249
intraventricular haemorrhage	10022840
iris haemorrhage	10057418
joint microhaemorrhage	10077666
lacrimal haemorrhage	10069930
large intestinal haemorrhage	10052534
laryngeal haemorrhage	10065740
lip haemorrhage	10049297
lower gastrointestinal haemorrhage	10050953
lymph node haemorrhage	10074270
mediastinal haemorrhage	10056343
mesenteric haemorrhage	10060717
mouth haemorrhage	10028024
mucocutaneous haemorrhage	10076048
mucosal haemorrhage	10061298
muscle haemorrhage	10028309
myocardial haemorrhage	10048849
naevus haemorrhage	10062955
ocular retrobulbar haemorrhage	10057571
oesophageal haemorrhage	10030172
optic disc haemorrhage	10030919
optic nerve sheath haemorrhage	10030941
ovarian haemorrhage	10065741
pancreatic haemorrhage	10033625
papillary muscle haemorrhage	10059164
parathyroid haemorrhage	10059051

Preferred term	PT code
parotid gland haemorrhage	10051166
pelvic haemorrhage	10063678
penile haemorrhage	10034305
pericardial haemorrhage	10034476
periorbital haemorrhage	10071697
peritoneal haemorrhage	10034666
Petechiae	10034754
pharyngeal haemorrhage	10034827
pituitary haemorrhage	10049760
post procedural haemorrhage	10051077
procedural haemorrhage	10071229
prostatic haemorrhage	10036960
pulmonary alveolar haemorrhage	10037313
pulmonary haemorrhage	10037394
putamen haemorrhage	10058940
rectal haemorrhage	10038063
renal haemorrhage	10038460
respiratory tract haemorrhage	10038727
retinal haemorrhage	10038867
retroperitoneal haemorrhage	10038980
scleral haemorrhage	10050508
skin haemorrhage	10064265
small intestinal haemorrhage	10052535
soft tissue haemorrhage	10051297
spermatic cord haemorrhage	10065742
spinal cord haemorrhage	10048992
spinal epidural haemorrhage	10049236
spinal subarachnoid haemorrhage	10073564
spinal subdural haemorrhage	10073563
splenic haemorrhage	10041647
spontaneous haemorrhage	10074557
subarachnoid haemorrhage	10042316
subdural haemorrhage	10042364
testicular haemorrhage	10051877
thalamus haemorrhage	10058939
thoracic haemorrhage	10062744
thyroid haemorrhage	10064224
tongue haemorrhage	10049870
tracheal haemorrhage	10062543
upper gastrointestinal haemorrhage	10046274
ureteric haemorrhage	10065743

Preferred term	PT code
urethral haemorrhage	10049710
urinary bladder haemorrhage	10046528
urogenital haemorrhage	10050058
uterine haemorrhage	10046788
vaccination site haemorrhage	10069475
vaginal haemorrhage	10046910
venous haemorrhage	10065441
vitreous haemorrhage	10047655
vulval haemorrhage	10063816

THROMBOCYTOPENIA

Preferred term	PT code
bleeding time abnormal	10049227
bleeding time prolonged	10005140
coagulation test abnormal	10063557
platelet count abnormal	10035526
platelet count decreased	10035528
platelet disorder	10035532
platelet dysfunction	10073391
Thrombocytopenia	10043554
thrombocytopenic purpura	10043561

LOWER RESPIRATORY TRACT INFECTION

Preferred term	PT code
atypical pneumonia	10003757
Bronchitis	10006451
bronchitis viral	10053160
haemorrhagic pneumonia	10077933
lower respiratory tract infection	10024968
lower respiratory tract infection viral	10065188
lung infection	10061229
Pneumonia	10035664
pneumonia respiratory syncytial viral	10035732
pulmonary sepsis	10051739
respiratory syncytial virus bronchiolitis	10038718
respiratory syncytial virus bronchitis	10069811
respiratory tract infection	10062352
respiratory tract infection viral	10062106

